5.3 Secondary Effectiveness Endpoints

The secondary effectiveness endpoints include the following:

1. Increase in percentile ranking on the CDC growth chart for height at 12 months post implant or until the valve is removed/replaced due to anatomical growth of the subject, whichever occurs first, compared to baseline.
2. Increase in percentile ranking on the CDC growth chart for weight at 12 months post implant or until the valve is removed/replaced due to anatomical growth of the subject, whichever occurs first, compared to baseline.

CDC growth charts are provided in Appendix 3.

6 STATISTICAL ANALYSIS

6.1 Statistical Analysis and Reporting

Kaplan-Meier adverse event rates with 95% confidence intervals and early rates will be calculated for all safety and survival endpoints.

Hemodynamic function will also be evaluated at each visit for each of the following variables:

- Mean pressure gradients across the mitral valve
- Peak pressure gradients across the mitral valve
- Cardiac output
- Cardiac index
- Valvular regurgitation (and the site, as appropriate)

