5 ENDPOINTS

5.1 Primary Safety Endpoint

The primary safety endpoint for this study is the actuarial (Kaplan-Meier) rate of total valve-related adverse events experienced through 365 days post implant or until the valve is removed/replaced due to anatomical growth of the subject, whichever occurs first. Valve-related adverse events to be evaluated are:

- Death
- Endocarditis
- Hemorrhage (whether or not due to anticoagulant/antiplatelet medication) [all and serious]
- Nonstructural dysfunction (including perivalvular leak [all and serious], hemolysis, and hemolytic anemia)
- Reoperation (including valve explant, not due to anatomical growth of the subject) [all and valve-related]
- Structural valve deterioration
- Thromboembolism
- Valvular thrombosis

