7.2 Potential Risks

Potential risks of receiving a mechanical mitral valve include:

- The need for a second valve replacement due to either dehiscence, valve failure or malfunction, development of mitral stenosis, unacceptable hemodynamic status or eventual somatic outgrowth.
- Heart failure requiring cardiac transplant.
- Cardiac arrhythmia with or without the need of pacemaker implantation.
- Hemolysis potentially resulting in anemia with or without splenomegaly and/or development of cholelithiasis.
- Infection including but not limited to endocarditis, myocarditis, cellulitis and/or septicemia.
- Thromboembolism or hemorrhage causing stroke, myocardial infarction or other significant impairment.
- Obstruction or distortion of adjacent cardiac structures.

All of the identified risks have the potential to result in death. The mortality rate reported for mitral valve replacement in the pediatric population is highly variable and ranges between approximately 5 and 30%.^{3,7,12-15}

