9.2 Assessment Schedule

All enrolled subjects will be assessed according to the following schedule for as long as the valve is implanted.

Table 1: Assessment Schedule

ASSESSMENTS	Baseline	Procedure	Post-Procedure ¹ (+ 24 hours)	30 Days ¹ (± 14 days)	6 Months ¹ (± 30 days)	12 Months ¹ (± 60 days)	Annual Visits through 60 Months ¹ (± 60 days)	Explant (Prior to procedure)
Medical History	X							
Physical Exam (PE)	X		X	X	X	X	X	X
Transthoracic Echocardiogram (TTE) ²	X		X	X	X	X	X	X
Blood Collection ³	X		X	X	X	X	X	X
Anticoagulant/Antiplatelet Medication Collection	X	X	X	X	X	X	X	X
Adverse Event Collection ⁴		X	X	X	X	X	X	X
Adverse Event Follow-up ⁵			X	X	X	X	X	X

1. Visits are to occur as long as the valve remains implanted.
2. The study specifies TTE rather than transesophageal echocardiography (TEE) to minimize subject risk. Echocardiographic data collected from TEE warranted for any other medical purpose is allowed.
3. Plasma free hemoglobin for hemolysis evaluation. Spot urine urobilinogen is an acceptable alternative if a non-hemolyzed blood sample cannot be obtained.
4. Refer to section 15.2 for a list of adverse events that are required to be collected and reported.
5. Required only for subjects who have an unresolved adverse event.

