15.2.2 Reporting Valve-Related Adverse Events

Safety surveillance within this trial (and the safety reporting performed by the investigator) starts:

- as soon as the subject is enrolled for Pivotal IDE subjects enrolled under protocol revision A or B.
- as soon as the subject is enrolled for Adjunctive Prospective Subjects.
- from the time of attempted initial implant (defined as the device physically contacting the subject's cardiac anatomy) for enrolled Adjunctive EU/CU Subjects.

Safety surveillance and safety reporting will continue until the last study visit has been performed, or the subject is deceased, or the subject concludes participation in the trial.

Investigators are responsible for promptly reporting, as soon as they become aware, all serious and non-serious valve-related adverse events as specified in Akins et al.²⁵ to the sponsor by

completing the Adverse Event CRF. Serious adverse events should be reported as specified in Section 15.2.1. Reportable events include:

- Death
- Endocarditis
- Hemorrhage (whether or not due to anticoagulant/antiplatelet medication)
- Nonstructural dysfunction (including perivalvular leak, hemolysis, and hemolytic anemia)
- Reoperation (including valve explant, not due to anatomical growth of the subject)
- Structural valve deterioration
- Thromboembolism (valve-related)
- Valvular thrombosis
- Unanticipated Adverse Device Effects (UADEs)

Refer to Appendix 11 for definitions of all reportable valve-related adverse events. All unresolved adverse events should be followed by the Investigator until resolution. Updates to adverse events should be provided to the sponsor by completing the AE Follow-Up CRF.

The sponsor may request that additional information such as operative notes, clinic notes, discharge summaries, histopathology reports, or a physician's summary of the event be provided to the sponsor as supporting documentation for all reported events.

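### Kaplan-Meier rates for single non-fatal complications can only censor death and explant, so they lie at or above the actual probability of each complication; the composite primary endpoint is largely unaffected

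*Combined protocol and SAP*

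**What the plan says.** The safety analysis in section 6.1 is a single sentence: "Kaplan-Meier adverse event rates with 95% confidence intervals and early rates will be calculated for all safety and survival endpoints".

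Section 5.1 supplies the endpoint: "The primary safety endpoint for this study is the actuarial (Kaplan-Meier) rate of total valve-related adverse events experienced through 365 days post implant". The window can close earlier, "until the valve is removed/replaced due to anatomical growth of the subject, whichever occurs first". The section then lists eight event types. Three entries carry paired sub-rates, for example "Hemorrhage (whether or not due to anticoagulant/antiplatelet medication) [all and serious" and "Reoperation (including valve explant, not due to anatomical growth of the subject) [all and valve-related" (the third is perivalvular leak). Such pairs make sense only if rates are reported by type as well as for the total.

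Observation of the study valve stops at explant and at death. The first note to Table 1 in section 9.2 says "Visits are to occur as long as the valve remains implanted", and section 15.2.2 says "Safety surveillance and safety reporting will continue until the last study visit has been performed, or the subject is deceased".

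Nowhere do the documents say how a child who dies or is explanted enters the curve for a complication that has not yet occurred. No cumulative incidence or other competing-risk method is mentioned.

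**The concern.** A Kaplan-Meier curve for one complication, say valvular thrombosis, recognises only events and censoring. A child who dies or has the valve removed without thrombosis can no longer have it on the study valve, yet the estimator treats that child as still at the risk of those who remain. One minus Kaplan-Meier then describes a setting in which nobody dies or is explanted, not what happens to implanted children.

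Such exits are expected here. Section 7.2 describes reported mortality as "highly variable and ranges between approximately 5 and 30" percent and lists outgrowing the valve among the risks. Section 1.3 expects repeat replacement in very young children. What is at stake is whether each component rate can be read as the share of implanted children who have that complication. The bias runs in one direction, and the planned confidence interval does not reflect it.

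**Working it through.** The plan states no sample size, target rate or component rate, so there is no figure of its own to reproduce. The check covers direction first, then size.

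**Direction.** At each complication time let *a* be the number of complications and *n* the number at risk.

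- One minus Kaplan-Meier = Σ S_KM(t−) · a/n, where S_KM drops only at complications.
- Aalen-Johansen cumulative incidence = Σ S_all(t−) · a/n, where S_all drops at complications, deaths and explants.

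S_KM is never below S_all, so every term of the first sum is at least as large. The two are equal only if no death or explant precedes a later complication.

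**A small invented example.** Take 20 children, with deaths or explants on days 10, 20, 30, 150 and 250, complications on days 25, 90, 200 and 300, and 11 event-free at day 365. The numbers at risk at the complications are 18, 16, 14 and 12.

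- One minus Kaplan-Meier = 1 − (17/18)(15/16)(13/14)(11/12) = 24.6%.
- Actual proportion with the complication = 4/20 = 20.0%, which is also the Aalen-Johansen estimate.

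**Size: inputs.**

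- Mortality *m* = 5%, 15%, 30%. The ends are the range in section 7.2 and the middle value is chosen. Section 7.2 gives no time horizon; applying the range to the horizon of the component rate is an assumption.
- Kaplan-Meier component rate *q* = 15%: assumed.
- Constant, independent hazards: assumed.

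**Formulas.** h = −ln(1 − q) = 0.1625 and d = −ln(1 − m). Cumulative incidence = h/(h + d) × [1 − (1 − q)(1 − m)]. In the limiting case where all deaths precede any complication, it is q(1 − m).

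| m | d | Constant hazards | Gap (points) | Limiting case |
|---|---|---|---|---|
| 5% | 0.0513 | 0.1625/0.2138 × 0.1925 = 14.6% | 0.4 | 0.15 × 0.95 = 14.3% |
| 15% | 0.1625 | 0.5 × 0.2775 = 13.9% | 1.1 | 0.15 × 0.85 = 12.8% |
| 30% | 0.3567 | 0.1625/0.5192 × 0.405 = 12.7% | 2.3 | 0.15 × 0.70 = 10.5% |

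**Explant.** The documents give no rate of growth explant. If 10% is assumed (g = −ln 0.90 = 0.1054, added to the hazards, with 0.90 added to the product), the constant-hazard figures become 13.9%, 13.2% and 12.1%. The 40% re-operation figure in section 1.3 is not used for size: it has no horizon and does not separate growth from complications.

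**Which way the death figures lean.** The formulas treat every death as competing. Under Appendix 11 a death due to thrombosis, embolism, bleeding or endocarditis follows that complication, so it does not compete with it. Thrombosis found at autopsy after an unrelated death is also counted. Many non-growth explants will likewise follow the complication that prompted them. The gaps therefore lean towards upper bounds.

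**The case against.** The strongest reply has four parts.

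*The censoring is inferred.* This is true: no section states it, and the per-type curves are themselves read from section 6.1 and the bracketed sub-rates. But the named method leaves no other way for these children to enter, and observation does stop at death and explant.

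*Section 5.1 names the actuarial rate deliberately, and risk while the valve is in place is a legitimate question.* This stands as a reason to keep the Kaplan-Meier figure. It is not a reason to leave out the rate that describes what happened.

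*The gap is small beside sampling error.* This largely stands at low competing risk. The binomial standard error of a 15% rate, √(0.15 × 0.85/N), is about 8.0 points at N = 20 and 3.6 at N = 100 (both N assumed), against a gap of 0.4 to 2.3 points. No performance goal is attached to a component, so no stated decision would change. The bias also makes the device look worse, not safer.

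*Components would not sum to the composite under either method.* This is correct. A child can have several complications, so additivity is no argument for the change.

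A reader might infer that the primary safety result is biased in the same way. The documents do not support that: section 5.1 lists death and non-growth reoperation as events in the total. Only growth explant could compete there, and non-valve death if it is not counted. Nor do the documents say that product labelling will quote component rates.

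**Conclusion.** The concern holds for the individual non-fatal components. Their Kaplan-Meier rates will be at or above the actual probability of the complication, and equal to it only when no death or explant precedes a later complication. On a 15% rate, with section 7.2 mortality taken over the same horizon and constant independent hazards, the overstatement from death is about 0.4 to 2.3 points. If all deaths precede any complication, it is about 0.8 to 4.5 points (15 − 14.25 and 15 − 10.5).

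A reader might take from the limiting case that rates are inflated by up to 43% (15/10.5 = 1.43). That needs 30% mortality, all of it before the first complication, so it is not an expected size. A reader might also expect the gap to widen by five years. That is plausible if explants accumulate, but the documents give no timed rates from which to compute it.

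This is a cheap improvement to component reporting, not a flaw in the primary endpoint.

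**What to change.** Add to section 6.1:

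- For each non-fatal component, report the Aalen-Johansen cumulative incidence with 95% CI, with death and explant occurring before that complication as competing events.
- For reoperation, non-growth explant is the event itself, so only death and growth explant compete. Treating every explant as competing would remove events from this component and understate it.
- Show the actuarial Kaplan-Meier component rate beside it for comparison with published series.
- Keep Kaplan-Meier for survival and for the composite primary safety endpoint.
- State the censoring rules for each.

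The cost is plan wording and one more table column. No new data are needed, since dates of death, explant and each event are already required for the planned analysis. The downside is two rates per component, with a footnote to explain the difference.

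Label: cheap improvement.

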7 RISK/BENEFIT ANALYSIS

7.1 Potential Benefits

Replacement of a diseased mitral valve with the 15mm MHV may improve hemodynamic function of the valve thereby providing the opportunity for improved physical growth and development. An additional potential benefit of receiving an appropriately sized mitral valve replacement is avoidance of complications associated with implantation of a mitral prosthesis too large for the size of the annulus which may include damage to the conductive system, obstruction of the left ventricular outflow tract (LVOT), impairment of valve mobility, and damage to the left circumflex artery.

7.2 Potential Risks

Potential risks of receiving a mechanical mitral valve include:

- The need for a second valve replacement due to either dehiscence, valve failure or malfunction, development of mitral stenosis, unacceptable hemodynamic status or eventual somatic outgrowth.
- Heart failure requiring cardiac transplant.
- Cardiac arrhythmia with or without the need of pacemaker implantation.
- Hemolysis potentially resulting in anemia with or without splenomegaly and/or development of cholelithiasis.
- Infection including but not limited to endocarditis, myocarditis, cellulitis and/or septicemia.
- Thromboembolism or hemorrhage causing stroke, myocardial infarction or other significant impairment.
- Obstruction or distortion of adjacent cardiac structures.

All of the identified risks have the potential to result in death. The mortality rate reported for mitral valve replacement in the pediatric population is highly variable and ranges between approximately 5 and 30%.^{3,7,12-15}

7.3 Risk Minimization

Risks will be minimized by selecting Investigators that:

- Have experience implanting mechanical mitral valves in patients under the age of five.
- Appreciate the need for closely monitoring and managing anti-coagulation regimens.
- Are willing to partner with the subject's personal cardiologist to ensure appropriate care and follow-up.

8 ELIGIBILITY CRITERIA

8.1 Eligibility Criteria for Pivotal IDE Subjects

A subject is eligible to participate in the study if he/she meets all inclusion criteria and meets no exclusion criterion.

8.1.1 Inclusion Criteria for Pivotal IDE Subjects

1. Subject requires mitral valve replacement.*
2. Subject's legally authorized representative gives written consent to participate in the clinical study.
3. Subject is willing and able to return for data collection and follow-up for the duration of the clinical study.

*Subjects undergoing concomitant procedures (e.g. valve repair) are eligible for this study other than those noted in the exclusion criteria.

8.1.2 Exclusion Criteria for Pivotal IDE Subjects

1. Subject is > 5 years of age.
2. Subject has a contraindication to anticoagulant/antiplatelet medication.
3. Subject has a prosthetic valve(s) at a site other than the mitral valve prior to the study procedure.*
4. Subject requires concomitant replacement of the tricuspid, pulmonary, or aortic valve.
5. Subject has active endocarditis.
6. Subject has active myocarditis.
7. Subject has had an acute preoperative neurological deficit that has not returned to baseline or stabilized ≥ 30 days prior to the study procedure.
8. Subject has had an acute cardiac adverse event that has not returned to baseline or stabilized ≥ 48 hours prior to the study procedure.
9. Subject has a non-cardiac illness resulting in a life expectancy of < 1 year.
10. Subject has a known requirement for additional cardiac surgery within 12 months after the study procedure.
11. Subject has been previously enrolled and implanted in this study.
12. Subject is participating in another study for an investigational drug and/or device.
13. Subject has any other medical condition that in the opinion of the Investigator will interfere with the study results.

*Subjects who have undergone a previous Ross procedure of the pulmonary valve are eligible for this study.

8.2 Eligibility Criteria for Adjunctive Subjects

In an effort to ensure data on all real-world use conditions are consistently collected and reported on, a subject is eligible to participate in protocol Revision C if he/she meets all of the following inclusion criteria and meets no exclusion criterion. Separate criteria are presented below for the two arms of adjunctive subjects of Revision C (Adjunctive Prospective Subjects in Sections 8.2.1 and 8.2.2 and Adjunctive EU/CU Subjects in Section 8.2.3).

8.2.1 Inclusion Criteria for Adjunctive Prospective Subjects

1. Subject requires mitral valve replacement.*
2. Subject's legally authorized representative gives written consent to participate in the clinical study.
3. Subject is willing and able to return for data collection and follow-up for the duration of the clinical study.

*Subjects undergoing concomitant procedures (e.g. valve repair) are eligible for this study.

8.2.2 Exclusion Criteria for Adjunctive Prospective Subjects

1. Subject is > 5 years of age.
2. Subject has a contraindication to anticoagulant/antiplatelet medication.

8.2.3 Eligibility Criteria for Adjunctive EU/CU Subjects

In order for Adjunctive EU/CU Subjects with a previous implant attempt to be eligible for study participation, the following criteria must be met:

1. The subject must have been ≤ 5 years of age at the time of mitral valve replacement with the 15mm MHV.
2. An implant was attempted with the 15mm MHV, where implant attempt is defined as the device physically contacting the subject's cardiac anatomy.
3. The legally authorized representative signs the study informed consent for this protocol allowing access to all relevant historical medical information and prospective follow-up (if applicable).
4. Either
 - (a) the legally authorized representative and site agree to follow the subject per the assessment schedule and complete all required assessments per this protocol from the time of consent going forward.
OR
 - (b) the subject's status is deceased or explanted, but an implant with 15mm MHV was attempted.

9 STUDY PARTICIPATION

9.1 Screening and Informed Consent

This study will be performed in accordance with applicable confidentiality, privacy and security, and data protection laws. The subject's legally authorized representative must provide written informed consent prior to performing any protocol-required baseline testing that is not standard of care for valve procedures.

9.2 Assessment Schedule

All enrolled subjects will be assessed according to the following schedule for as long as the valve is implanted.

Table 1: Assessment Schedule

ASSESSMENTS	Baseline	Procedure	Post-Procedure ¹ (+ 24 hours)	30 Days ¹ (± 14 days)	6 Months ¹ (± 30 days)	12 Months ¹ (± 60 days)	Annual Visits through 60 Months ¹ (± 60 days)	Explant (Prior to procedure)
Medical History	X							
Physical Exam (PE)	X		X	X	X	X	X	X
Transthoracic Echocardiogram (TTE) ²	X		X	X	X	X	X	X
Blood Collection ³	X		X	X	X	X	X	X
Anticoagulant/Antiplatelet Medication Collection	X	X	X	X	X	X	X	X
Adverse Event Collection ⁴		X	X	X	X	X	X	X
Adverse Event Follow-up ⁵			X	X	X	X	X	X

1. Visits are to occur as long as the valve remains implanted.
2. The study specifies TTE rather than transesophageal echocardiography (TEE) to minimize subject risk. Echocardiographic data collected from TEE warranted for any other medical purpose is allowed.
3. Plasma free hemoglobin for hemolysis evaluation. Spot urine urobilinogen is an acceptable alternative if a non-hemolyzed blood sample cannot be obtained.
4. Refer to section 15.2 for a list of adverse events that are required to be collected and reported.
5. Required only for subjects who have an unresolved adverse event.

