3.1 Study Duration

Each enrolled subject will be assessed at baseline, procedure, post-procedure, 30 days, six months, 12 months, and annually thereafter for as long as the valve remains implanted. Each enrolled subject will be followed for five years from the date of implant, until subject withdrawal, or until study closure, whichever occurs earliest.

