4.2 Objective

The objective of this study is to evaluate the safety and effectiveness of the 15mm MHV in subjects five years or less of age with a diseased, damaged, or malfunctioning mitral heart valve. The objective will be evaluated by assessing valve-related adverse events, subject survival, subject growth, and echocardiogram assessment of hemodynamic function through the five year follow-up visit as long as the valve remains implanted.

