5.2 Primary Effectiveness Endpoints

The primary effectiveness endpoints in this study include the following:

1. Survival at 12 months post implant or survival until the valve is removed/replaced due to anatomical growth of the subject, whichever occurs first.
2. Peak gradient as assessed by echocardiography at 12 months post implant or when the valve is removed/replaced due to anatomical growth of the subject, whichever occurs first.
3. Mean gradient as assessed by echocardiography at 12 months post implant or when the valve is removed/replaced due to anatomical growth of the subject, whichever occurs first.

4. Valvular regurgitation as assessed by echocardiography at 12 months post implant or when the valve is removed/replaced due to anatomical growth of the subject, whichever occurs first.

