9.7 Additional Follow-up

Protocol required follow-up visits should be completed by the Investigator. To aid in subject follow-up compliance, subjects can return to their primary cardiologist for follow up visits but data must be obtained by the Investigator for review and submission to the Sponsor.

Investigators should inform cardiologists of all required follow-up tests prior to the visit and every effort should be made to obtain complete tests results with all required data points after the visit occurs. Protocol deviations will be required for all missed testing (refer to section 17.2.5 Protocol Compliance).

The following assessments are required at follow-up visits at the intervals noted on the assessment schedule in section 9.3 for all enrolled subjects that have the valve implanted:

- Physical exam
- Transthoracic echocardiogram
- Blood collection (Plasma free hemoglobin for Hemolysis evaluation). Spot urine urobilinogen is an acceptable alternative if a non-hemolyzed blood sample cannot be obtained.
- Anticoagulant/antiplatelet medication collection
- Adverse event collection
- Adverse event follow-up

For Adjunctive EU/CU Subjects, additional assessments should be collected from subject's medical records, when available, for visits conducted prior to enrollment.

10 Discontinuation

Subjects must be informed about their right to withdraw from the study at any time and for any reason without sanction, penalty, or loss of benefits to which the subject is otherwise entitled. Withdrawal from the study will not jeopardize the subject's future medical care or relationship with an Investigator. All reasonable efforts should be made to retain the subject in the clinical study until study completion. Subjects will be asked what the reason for termination/withdrawal is but have the right not to answer.

The Principal Investigator may also withdraw a subject from the study at any time if he/she believes it is in the subject's best interest.

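### Primary 12-month survival continues after a non-growth explant, but no vital-status check is required after explant and section 6.1 gives no rule for these children

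*Combined protocol and SAP*

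**What the plan says.** Section 5.2 defines the first primary effectiveness endpoint as "Survival at 12 months post implant or survival until the valve is removed/replaced due to anatomical growth of the subject, whichever occurs first". Explant for thrombosis, endocarditis, leak or dysfunction does not end it. Section 5.1 uses the same growth-only stop for safety and counts a non-growth explant as an event there.

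The schedule is tied to the valve. Section 9.2 opens with "All enrolled subjects will be assessed according to the following schedule for as long as the valve is implanted". Footnote 1 to Table 1, which covers the 12-month column, adds "Visits are to occur as long as the valve remains implanted". The one explant visit is held before the explant operation. Section 9.7 requires follow-up assessments "for all enrolled subjects that have the valve implanted". The objective in section 4.2 assesses outcomes, survival among them, "through the five year follow-up visit as long as the valve remains implanted".

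Other passages point towards longer follow-up. Section 3.1 states: "Each enrolled subject will be followed for five years from the date of implant, until subject withdrawal, or until study closure, whichever occurs earliest". Explant is not listed there as an end of follow-up, although the sentence before it limits assessments to the time the valve is in place. Section 10 says: "All reasonable efforts should be made to retain the subject in the clinical study until study completion". Section 15.2.2 has unresolved adverse events followed to resolution, section 15.2.4 requires reports of deaths during the study, and Appendix 11 says all deaths will be reported and classified.

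Section 6.1 prescribes Kaplan-Meier rates with 95% confidence intervals for safety and survival endpoints. It has no rule for explant.

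**The concern.** The endpoint needs a status that the schedule does not collect. After a non-growth explant no visit or contact is required, so a fully compliant site may not know at 12 months whether the child is alive. These are the children whose valve failed, so their missing status is unlikely to be unrelated to survival.

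The reported figure then depends on a choice the plan does not state:

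- **Censor all at explant.** Survival is overstated or understated, depending on mortality after explant.
- **Count as alive at last contact.** Survival is overstated whenever a death goes unrecorded.
- **Record deaths that come to notice but censor survivors at explant.** Survival is understated.

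The confidence interval reflects none of this. Section 4.2 can even be read as assessing survival only while the valve is in place, which is not what section 5.2 says. The composite safety endpoint is little affected, because a non-growth explant is already an event there.

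**Working it through.** The supplied text gives no sample size, performance goal, non-growth explant rate or post-explant mortality, so there is no figure of the plan's own to reproduce. What follows shows scale only.

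**Inputs (all assumed)**

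- p, 12-month mortality with the valve in place: 5%, 15%, 30%. The range comes from section 7.2, which gives no time horizon; its use at 12 months is an assumption.
- e, non-growth explant by 12 months in the absence of death: 5%, 10%, 20%.
- q, death between explant and day 365 among explanted children: 0, 5, 10, 15, 20, 30%.
- Constant competing hazards over the year.

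**Formulas**

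- ld = −ln(1−p), le = −ln(1−e), L = ld + le
- Died with valve in place: D = (ld/L)(1−exp(−L))
- Explanted: E = (le/L)(1−exp(−L))
- True 12-month mortality: D + E·q
- Reported mortality: (1) all censored at explant, p; (2) counted alive, D; (3) deaths captured soon after explant and survivors censored at explant, 1 − (1−p)(1−e)^q
- Bounds: all alive, D; all dead, D + E

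**Middle case (p = 15%, e = 10%, q = 20%)**

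ld = 0.1625, le = 0.1054, L = 0.2679, exp(−L) = 0.765.
D = (0.1625/0.2679) × 0.235 = 14.26%; E = (0.1054/0.2679) × 0.235 = 9.24%.

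| Quantity | 12-month mortality |
|---|---|
| True: 14.26 + 9.24 × 0.20 | 16.11% |
| (1) Censored at explant | 15.00% |
| (2) Counted alive | 14.26% |
| (3) Deaths captured, survivors censored: 1 − 0.85 × 0.90^0.2 | 16.77% |
| Bounds, all alive to all dead | 14.26% to 23.50% |

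If only a share c of post-explant deaths is captured, replace q by q·c in (3). True minus reported is +1.11 points at c = 0, +0.21 at 50%, −0.23 at 75% and −0.67 at 100%; the sign changes near c = 62%.

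**Whole grid, true minus reported mortality**

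- (1) −2.9 to +5.3 points. Break-even q = (p − D)/E is about 2.6%, 8% and 17% at p = 5%, 15% and 30%.
- (2) 0 to +5.9 points.
- (3) −2.9 to −0.1 points. Excluding q = 0, the lower end is still −2.9.

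Simulations of three cases, with captured deaths spread from explant to day 365, gave 16.8%, 34.7% and 11.4% under (3), against true values of 16.1%, 32.2% and 10.3%: the same direction as the formula.

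**Small-sample illustration (assumed N = 20)**

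Three deaths with the valve in place (days 30, 120, 210) and four non-growth explants (days 90, 120, 150, 180). Censoring at explant gives survival of (19/20)(17/18)(13/14) = 83.3%, with a log-log 95% interval of 56.3% to 94.4%. Following the four children to day 365 gives 17/20 = 85%, 15/20 = 75% or 13/20 = 65% if 0, 2 or 4 of them die.

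**Sampling error for comparison**

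Half-width 1.96 × √(0.16 × 0.84/N) is 16.1 points at N = 20 and 10.2 at N = 50. Each child of unknown status widens the bounds by 1/N, that is 5 to 2 points.

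**The case against.** The strongest reply is that deaths are better covered than the visit table suggests. Appendix 11 says all deaths are reported and includes death due to reintervention among valve-related deaths; sections 3.1 and 15.2.4 point the same way. Deaths around the explant operation should therefore often reach the sponsor. That stands, but all of this is passive. It confirms no survivor, and it leaves open whether an explanted child is still in the study. Section 8.2.3 even sets explanted beside deceased as the alternative to agreed follow-up, though only for the Adjunctive EU/CU arm. Capturing deaths without confirming survivors is handling (3), which has its own bias.

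Second, the effect is small beside sampling error. Under censoring at explant, the median absolute bias over the 54 grid cells is 0.6 points, 81% of cells are under 2 points, and the 5.3-point extreme is a single corner. No success criterion in the text is shown to turn on it. This stands and limits the severity.

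Third, the break-evens depend on constant hazards. If valve-in-place deaths come before explants, censoring can only understate mortality: in the middle case, true mortality is 15 + 85 × 0.10 × 0.20 = 16.7% against 15.0% reported. This also stands. The conclusion that direction is unknown does not need the break-evens, because handlings (2) and (3) err in opposite directions.

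Fourth, ruling out censoring at explant could be called choosing the estimand for the sponsor. It only applies section 5.2 as written.

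**Conclusion.** The concern holds. Section 5.2 requires 12-month survival after a non-growth explant, sections 9.2 and 9.7 require no assessment after it, and section 6.1 is silent on how to analyse it. This is a conflict between a stated endpoint and a stated schedule, and it should be fixed. Confidence is high on the text. On size, the evidence is illustrative only: differences between true and reported mortality run from about −3 to +6 points across the three handlings, under assumed mortality, explant rate, post-explant mortality and, for the formulas, constant hazards. The error is likely to be smaller than sampling error at the assumed sample sizes, but the interval does not show it.

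**What to change.** 1. Reconcile sections 3.1, 4.2, 9.2, 9.7 and 15.2.2 with section 5.2. State that a subject with a non-growth explant remains in the study for vital status, obtained by phone or from records at day 365 post implant.
2. In section 6.1, state that for the survival endpoint these subjects are followed to day 365 and not censored at explant.
3. Report the number with unknown day-365 status, with an all-alive/all-dead sensitivity analysis. A valve-in-place analysis may be given as supplementary.

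The cost is protocol and analysis wording plus one contact or record check per affected child. The amendment may need FDA and IRB/EC approval under section 17.1.2, and children already explanted may have to be re-contacted or their consent checked. The survival figure may become slightly less favourable.
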